The subject is then randomized to a study treatment and begins therapy in the CRU. The assigned study treatment will be 4 weeks in duration. They are initially provided with a 1-week supply of blinded study drug and OmniPods. The subjects will return weekly for a safety check, CGM device data retrieval, new sensor insertion, and receipt of study supplies. The subject is expected to complete at least 90% of the study therapy during the 4-week treatment period.

After 4 weeks of study therapy, the subject will return to the clinic. The study product will be stopped and the CGM data retrieved before a repeat of the hypoglycemia induction procedure as described above.

After 12 weeks after study treatment, the subjects will return to the CRU for insertion of a CGM device. One week later (13 weeks after completing study treatment), the CGM will be retrieved and the subject will undergo the hypoglycemia induction procedure as described above.

After 25 weeks after study treatment, the subjects will return to the CRU for insertion of a CGM device. One week later (26 weeks after completing study treatment), the CGM will be retrieved and the subject will undergo the hypoglycemia induction procedure as described above.

After completion of the hypoglycemia induction procedure at 26 weeks, the subject's participation in the study is completed.

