### **9.5.3. Visit 3 (Day 1) Start of Treatment Phase**

The subject will arrive to the clinic at about 6-9 am for the planned randomization. The subject will fast after midnight until the end of the hypoglycemia procedure the subsequent day.

The following procedures will be completed:

1. Eligibility Review
2. The subject's CGM, electronic diary, and insulin utilization data will be collected/uploaded to the electronic data capture (EDC).
3. Assessment will be made whether the CGM baseline data meet the criteria of minimum 6 days are recorded using the CGM device. The clinic will be notified within 30 minutes from time of subject data upload as follows:
  - a. If the data do not meet the above criteria, the subject is inserted with another CGM for renewed baseline of CGM period. The visit is rescheduled for a week later and the subject is sent home with instructions for another baseline attempt. Should the second baseline period not yield eligible CGM data, the subject will stop further participation in the procedures.
  - b. If the data meets criteria, the visit proceeds.

The following procedures will be carried out once CGM data is confirmed. This includes a confirmation that the subject did not have a hypoglycemic event, < 70 mg/dL during the 8 hours prior to the induction.

4. A new CGM sensor will be inserted.
5. The subject will be asked of any changes in concomitant medications since their last visit and this will be documented in the CRF.
6. The subject will fill out the Gold Score about hypoglycemia awareness.
7. Urine pregnancy test for women of childbearing potential.
8. The subject will be reminded to refrain from using his or her own insulin until the hypoglycemia induction procedure the following day is complete. However, the subject will withhold their long acting insulin.

9. The Insulin Diary will be collected from the previous visit and a new diary given to the subject to collect the following, daily:
  - Total daily dose
  - Total Daily Bolus
  - Basal Rate
10. IV lines are inserted in both upper extremities. One side will be used for both IV insulin infusion and IV glucose infusion. The other side will be used for venous sampling during the clamp procedure.
11. Collection of venous blood for the following tests as outlined in the Schedule of Activities:
  - CBC/CMP
  - Plasma glucagon (PK) prior to Omnipod placement

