12. Plasma glucose is measured using a laboratory quality instrument, e.g. the YSI 2300 or 2900 that will be used for the clamping procedure.
13. Insulin infusion should begin after the baseline venous blood samples are obtained. An IV glucose infusion should be started concomitantly.
14. Assessment of vital signs, including measurement of BP, after a 5-minute seated rest
15. The 100 mg/dL baseline prior to hypoglycemia induction will be assessed for adequacy or initiated as described in section 9.4.1.
  - a. When the baseline has been deemed adequate for at least 60 minutes two sets of blood samples for assessment of counter regulatory hormones will be drawn 10 minutes apart and processed.
16. The hypoglycemia induction including PG determination and hypoglycemia symptoms assessments (Appendix 2) will be executed as described in sections 9.4.2 to 9.4.5.
17. When hypoglycemia at 50 mg/dL has been held for 30 minutes, two sets of blood samples for assessment of counter regulatory hormones will be drawn 10 minutes apart and processed.
18. Treatment allocation and dispensing: The subject will be randomized as described in section 8.4, investigational product and Omnipods for the subject will be retrieved from storage.
19. When PG is >70 mg/dL in the normalization phase (section 9.4.6) the subject will be instructed in the filling and deployment of the OmniPod.
20. The study personnel will ensure the Omnipod flow rate is correctly set per protocol.
21. The subject will fill and deploy the first Omnipod under the observation of study personnel, insert and initiate the device as part of the training so that the subject can do this at home 2-3 days later.
22. The subject will be supplied with sufficient investigational product, Omnipods, and other study materials until the next weekly visit. The subject's training will include instructions to prepare a new Omnipod with the study drug for insertion, every 2-3 days.
23. Each time a new OmniPod is started local tolerability will be assessed as follows:

- a. Subjects will complete a Visual Analog (VAS) questionnaire regarding infusion site discomfort ([Appendix 3](#)) at **10±5** minutes, at **30±5** minutes and again at **180±5** minutes following the injection of study drug.

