### **7.2.2 Duration/Study Day/Time**

Study day will be calculated as the number of days from first dose of study drug.

- date of event – date of first dose of study drug + 1, for events on or after day of first dose;
- date of event – date of first dose of study drug, for events before day of first dose.

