### 7.2.10 CGM Derived Parameters

CGM readings occur every 5 mins. Hence in a complete 24-hour period, 288 CGM readings would be captured. The following endpoints will be calculated per day (e.g., 24-hour period starting from CSGI injection).

- Proportional time spent with interstitial glucose < 70 mg/dL;
- Proportional time spent with interstitial glucose < 60 mg/dL;
- Proportional time spent with interstitial glucose < 50 mg/dL;
- Proportional time within  $70 \leq \text{interstitial glucose} < 180$  mg/dL;
- Proportional time with interstitial glucose  $\geq 180$  mg/dL.

Proportional time spent with  $IG < X$  mg/dL = (time spent with  $IG < X$  mg/dL (minutes) / total time spent with CGM (minutes)) \* 100 where  $x = 70, 60$  or  $50$ , given the continuous CGM readings.

- Rate of hypoglycemic event episodes at thresholds of plasma glucose <70 mg/dL;
- Rate of hypoglycemic event episodes at thresholds of plasma glucose <60 mg/dL;
- Rate of hypoglycemic event episodes at thresholds of plasma glucose <50 mg/dL;

Rate of hypoglycemic event episodes at thresholds of <X mg/dL is defined as the number of episodes with  $PG < X$  mg/dL, where 70, 60 or 50. Subsequent PG measures with the result of < X mg/dL should be considered as the same episode.

- Average interstitial glucose;
- Interstitial glucose standard deviation;
- Area over the curve (AOC) of the reduction from baseline in the interstitial glucose from T0 (defined as the date/time of the CSGI injection) to Tx, where x corresponds to time when interstitial glucose < 70, <60 and <50 mg/dL is achieved.

AOC calculations will be done using the standard trapezoidal rule

$$AOC = -\left(\sum_{i=0}^x \left(\frac{\text{abs}(\text{reduction in } IG_i) + \text{abs}(\text{reduction in } IG_{i+1})}{2}\right) * (T_{i+1} - T_i)\right)$$

Where:  $\text{abs}(\text{reduction in } IG_i)$  = absolute value of change from baseline in interstitial glucose at time i, and  $(T_{i+1} - T_i)$  is the Time difference in minutes between time i and time i+1.

For endpoints that will be calculated per day - baseline will be based on the CGM data collected on the latest day prior to the date/time of the first CSGI injection. For the AOC endpoint baseline will be the latest interstitial glucose measure obtained prior to the date/time of the first CSGI injection.

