**7.2.10.1 Weekly endpoints**

Additionally, all derived CGM endpoints will be derived on a weekly basis. The following weeks will be analyzed: Baseline (Week), Week 1, Week 2, Week 3, Week 4, Month 3 and Month 6. CGM-Derived parameters will be based on CGM data that fall in the following timeframe:

Week	Time window (Days)	
Baseline	7 days prior to day 1	
Week 1	1	7
Week 2	8	14
Week 3	15	21
Week 4	22	28
Month 3	7 days prior to date of Month 3 visit	
Month 6	7 days prior to date of Month 6 visit	

When deriving weekly endpoints - baseline will be based on the CGM data collected 7 days prior to the date/time of the first CSGI injection. For the AOC endpoint baseline will be the same as for the AOC calculated by day.

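### As worded, the SAP's CGM baseline takes in the Visit 3 hypoglycemia clamp while Week 4 contains no clamp, and the weekly table gives a conflicting window

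*SAP*

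**What the plan says.** **Baseline windows (SAP).** For daily endpoints, section 7.2.10 states that "baseline will be based on the CGM data collected on the latest day prior to the date/time of the first CSGI injection". For weekly endpoints, the text of 7.2.10.1 states that "baseline will be based on the CGM data collected 7 days prior to the date/time of the first CSGI injection", but the table in the same section gives baseline as "7 days prior to day 1", with Week 1 as Days 1-7 and Week 4 as Days 22-28. The Month 3 and Month 6 windows are the 7 days before the visit date. The baseline for the area over the curve (AOC) is the last interstitial reading before the first dose.

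**What a day is (SAP).** Section 7.2.10 uses a "24-hour period starting from CSGI injection". Section 7.2.2 counts by date: "Study day will be calculated as the number of days from first dose of study drug", so Day 1 is the date of the first dose.

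**Order of events (protocol).** In section 9.5.3 the run-in CGM data are uploaded at step 2. At step 4, "A new CGM sensor will be inserted". IV lines follow at step 10 and the clamp at steps 15-17. At step 19, once plasma glucose is above 70 mg/dL, "the subject will be instructed in the filling and deployment of the OmniPod"; the first pod is deployed at step 21. At Week 4 the order is reversed (section 7.1): "The study product will be stopped and the CGM data retrieved before a repeat of the hypoglycemia induction procedure". Table 6 shows no sensor insertion at Visits 7, 9 or 11.

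Neither document has a rule that excludes CGM readings taken during a clamp.

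**The concern.** The CGM objectives compare baseline with Week 4 for time below 70, 60 and 50 mg/dL and for episode rates, and then follow these over time. The baseline should describe the subject's usual glucose before treatment. Under the SAP text, its last hours instead describe a procedure: fasting, IV insulin and glucose, and a deliberate hold near 50 mg/dL. The Week 4 window has no counterpart to this.

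Three outputs are at stake: within-arm changes from baseline (placebo included), the by-day and by-week tables and figures, and the precision of the change scores. Clamp length varies between subjects because steps may be prolonged or restarted (protocol sections 9.4.1, 9.4.3 and 9.4.4), so procedure noise enters each change score in arms of 16. The AOC has its own problem: its starting value is a reading from around clamp recovery.

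The text and table of 7.2.10.1 also allow two programmers to produce different weekly results from the same data.

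**Working it through.** **1. The plan's own figure.** One reading every 5 minutes gives 24 × 60 / 5 = 288 per day, as SAP section 7.2.10 states. The denominators below are 1,440 minutes (day) and 10,080 minutes (week).

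**2. Where the Visit 3 clamp falls under each rule.**

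| Rule | Baseline | Week 1 | Week 4 |
|---|---|---|---|
| Text of 7.2.10 and 7.2.10.1 (clock time of first dose) | in | out | out |
| Weekly table, date-based days (7.2.2) | out | in | out |
| Weekly table, 24-hour days from first dose (7.2.10) | in | out | out |

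Each rule leaves the clamp in one of the analyzed windows. The Visit 7, 9 and 11 clamps are in none of them.

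**3. Is the new sensor likely to be recording?** From the start of stabilization to the second fall, the protocol schedules 60 min stabilization + 10 min between samples + 30 min fall from 100 to 70 mg/dL + 30 min plateau = 130 min. The sensor is inserted before all of this. A start-up delay of up to about 2 hours would therefore not remove the fall from 70 to 50 mg/dL or the hold. The documents give no start-up time, so this remains an assumption.

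**4. Gross clamp contribution.**

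Inputs from the protocol:
- Fall from 70 to 50 mg/dL at about 1 mg/dL per minute (Table 5): 20 min.
- Hold near 50 mg/dL to the second hormone sample (section 9.4.4): 30 + 10 = 40 min.

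Assumed inputs:
- Recovery to 70 mg/dL: 5-20 min.
- Part of the 30-minute plateau at 65-75 mg/dL that reads below 70: 0-30 min.
- Interstitial readings follow plasma glucose.

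Results:
- Below 70 mg/dL, low: 20 + 40 + 5 + 0 = 65 min; 65/1,440 = 4.5 points (day); 65/10,080 = 0.64 (week).
- Below 70 mg/dL, high: 20 + 40 + 20 + 30 = 110 min; 110/1,440 = 7.6 points (day); 110/10,080 = 1.09 (week).
- Below 60 mg/dL: 10 min fall + 40 min hold + an assumed 2-10 min recovery = 52-60 min; 3.6-4.2 points (day); 0.5-0.6 (week).
- Below 50 mg/dL: 0-40 min, depending on where glucose sits in the 45-55 range; 0-2.8 points (day); 0-0.4 (week).
- Episodes: at least one more below 70 and below 60 mg/dL, and possibly one below 50.

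**5. Net apparent change to Week 4 when nothing has truly changed.** Let p be usual time below 70 mg/dL, m the clamp minutes (65-110) and T the window in minutes. Assume 300 minutes in clinic replace ordinary time. Then baseline = [p(T − 300) + m]/T and apparent change = p − baseline. Section 9.5.3 also requires no event below 70 mg/dL in the 8 hours before induction. If that removes all such time for 480 minutes, T − 300 becomes T − 780. This offset is applied at Visit 3 only, where the protocol states it.

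Example with p = 6%, m = 65, daily, 8-hour rule: (0.06 × 660 + 65)/1,440 = 7.26%, a change of −1.26 points.

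Ranges over m = 65-110, in percentage points, with the 8-hour rule:

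| Assumed p | Daily baseline | 7-day baseline |
|---|---|---|
| 2% | −3.4 to −6.6 | −0.5 to −0.9 |
| 6% | −1.3 to −4.4 | −0.2 to −0.6 |
| 10% | +0.9 to −2.2 | +0.1 to −0.3 |
| 15% | +3.6 to +0.5 | +0.5 to +0.1 |

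With the 8-hour rule the change is zero when p = m/780, that is 65/780 = 8.3% to 110/780 = 14.1%. Without the offset, p from 2% to 15% gives −1.4 to −7.2 points (daily) or −0.2 to −1.0 (weekly). The documents give no value for p.

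**The case against.** **The intended window may be clean.** Protocol section 9.5.3 treats the run-in upload as the CGM baseline and checks it for 6 days of data before the new sensor goes in. The weekly table with date-based days agrees: it keeps the clamp out of both baseline and Week 4. The daily wording could also be read as the last full day before the dosing date. This stands as far as intent goes, and it means inclusion is not settled for the weekly endpoints. But the text names a date and time, and section 7.2.10 anchors its days on the injection. Followed literally, the text includes the clamp, and nothing says whether text or table governs.

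**The direction is not established.** A reader might infer that every arm, placebo included, must show a false fall in hypoglycemia. The documents do not support that: the 8-hour requirement lowers the same baseline and can cancel or reverse the effect. This stands.

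**The planned inference is between arms.** A reader might also infer a biased treatment effect. SAP section 7.10.4 compares arms by one-factor ANOVA, and the clamp precedes the first dose in all randomized arms, so its expected contribution cancels. Section 7.10.5 treats secondary endpoints as descriptive. This stands too; what remains is distorted within-arm description and added noise, which cannot be quantified from the documents.

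**The minutes in step 4 are gross.** They do not subtract the ordinary time that the clinic visit replaces. This is correct, and step 5 gives the net figures.

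**Conclusion.** The concern holds for the SAP text. The daily baseline, and the weekly baseline by its text, include the Visit 3 clamp; the Week 4, Month 3 and Month 6 windows contain none. The weekly table contradicts that text and, with date-based days, can count pre-dose induced hypoglycemia as Week 1.

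The gross effect is substantial against a one-day baseline and about 1 percentage point or less against a 7-day one. The net effect is a spurious fall if usual time below 70 mg/dL is low (assumed 2-6%), and can cancel or reverse at about 10% or more. These sizes rest on the assumed recovery time, plateau time, clinic time, usual time below 70 mg/dL and sensor recording.

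The damage is confined to within-arm changes, time-course displays, noise in the change scores and the AOC starting value. This should be fixed, but it does not threaten the epinephrine endpoint or the expected between-arm difference.

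**What to change.** In SAP sections 7.2.10 and 7.2.10.1:

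- Use one baseline definition in text and table, daily and weekly, ending when the run-in sensor is retrieved at Visit 3 (or at midnight before Visit 3).
- Start Day 1 and Week 1 at the start of the first pod, active or placebo.
- Exclude Visit 3 CGM readings from the start of IV insulin through the end of normalization from all windows. No such filter is needed for Visits 7, 9 and 11, where the windows already end before the clamp.
- Redefine the AOC baseline so that it is not a clamp-recovery reading, for example as a summary of run-in readings.

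The cost is SAP wording, one date/time filter in programming, and a few hours of CGM data per subject. Eligibility is unaffected, because the 6-day minimum is already assessed on the run-in upload.

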#### 4.2.1 Efficacy Endpoints

- Absolute change from Induction 1 (baseline visit) to Induction 2 (visit 7, Week 4) in plasma epinephrine concentration after 30 minutes of induced hypoglycemia with PG <50 mg/dL. The average of the non-missing results at each step will be used in analysis.
- Percent change from Induction 1 (baseline visit) to Induction 2 (visit 7, Week 4) in plasma epinephrine concentration after 30 minutes of induced hypoglycemia with PG <50 mg/dL by Diabetes Duration Category (<15 years, ≥15 years). The average of the non-missing results at each step will be used in analysis.
- Intravenous glucose infusion rate (GIR) [time frame: 0-30 mins induced hypoglycemia] (cumulative glucose infusion rate required to maintain insulin-induced hypoglycemia).
- Intravenous insulin infusion rate [time frame: 0-30 mins induced hypoglycemia] (cumulative insulin infusion rate required to maintain insulin-induced hypoglycemia).
- Change from Induction 1 (baseline visit) to Induction 2 (visit 7, Week 4) in other counter regulatory hormones (norepinephrine, glucagon, cortisol and growth hormone plasma concentrations) after 30 mins of induced hypoglycemia.
- Change from Induction 1 (baseline visit) to Induction 2 (visit 7, Week 4) in Neuroglycopenic Symptom Scores (if hypoglycemia present) as documented using the hypoglycemia symptom questionnaire.
- Change from Induction 1 (baseline visit) to Induction 2 (visit 7, Week 4) in Autonomic Symptom Scores (if hypoglycemia present) as documented using the hypoglycemia symptom questionnaire.
- Change from baseline to Week 4 in CGM-derived hypoglycemia parameters of:
  - Proportional time spent with interstitial glucose (IG) <70, 60, and 50 mg/dL;
  - Rate of hypoglycemic event episodes at thresholds of plasma glucose <70, 60, and 50 mg/dL.
  - Area over the curve (AOC) of the reduction from baseline in the interstitial glucose from T0 (defined as the date/time of the CSGI injection) to Tx, where x corresponds to time when interstitial glucose < 70, <60 and <50 mg/dL is achieved.
- Change from baseline to Week 4 in CGM-derived parameters of:
  - Average interstitial glucose and standard deviation;
  - Proportional time within  $70 \leq \text{interstitial glucose} < 180$  mg/dL;

- Proportional time with interstitial glucose  $\geq 180$  mg/dL.
- Change from Induction 1 (baseline visit) to Induction 2 (visit 7, Week 4) in the Gold scale as a measure of hypoglycemia awareness.

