### **5 SAMPLE SIZE**

The primary hypothesis is to evaluate change from Induction 1 (baseline visit) to Induction 2 (visit 7, Week 4) in plasma epinephrine concentration after 30 minutes of induced hypoglycemia with plasma glucose  $< 50$  mg/dL between treatment groups. Sample size is based on a closed hierarchical hypothesis test. Using this method, an alpha of 5% will be preserved for each hypothesis test where the next ordered test will only be conducted if statistical significance is achieved for that hypothesis.

Final calculations are based on 80% power and an alpha of 5%, to demonstrate a plasma epinephrine increase compared to placebo of 1.5 nmol/l given a SD of 1.34 nmol/l at an induced PG of 50 mg/dl. Sixteen subjects per treatment group (CSGI high dose, CSGI low dose, and placebo) are required based on the minimum sample size estimate for a comparison.

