### **6 RANDOMIZATION**

The randomization scheme is 1:1:1 for high dose, low dose and placebo. Each group will have 16 subjects, but the placebo group will be matched to high and low infusion rates (8 in each group). The randomization is stratified by site.

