14.2.2.7.2.1*	Change from Induction 1 (Baseline visit) in Average Neuroglycopenic Scores (ANS), Average Autonomic Scores (AAS) and Average Total Scores (ATS) with PG <50 mg/dl Intent-to-Treat Population	14.2.2.7.1.1
14.2.2.7.2.2*	Change from Induction 1 (Baseline visit) in Average Neuroglycopenic Scores (ANS), Average Autonomic Scores (AAS) and Average Total Scores (ATS) with PG <50 mg/dl Per Protocol Population	14.2.2.7.1.1
14.2.2.8.1.1	Summary of Overall Assessment of Hypoglycemia with PG <70 mg/dl Intent-to-Treat Population	
14.2.2.8.1.2	Summary of Overall Assessment of Hypoglycemia with PG <70 mg/dl Per Protocol Population	14.2.2.8.1.1
14.2.2.8.2.1	Summary of Overall Assessment of Hypoglycemia with PG <50 mg/dl Intent-to-Treat Population	14.2.2.8.1.1
14.2.2.8.2.2	Summary of Overall Assessment of Hypoglycemia with PG <50 mg/dl Per Protocol Population	14.2.2.8.1.1
14.2.2.9.1.1	Change from Baseline in CGM-Derived Hypoglycemia Parameters by Day - Intent-to-Treat Population	
14.2.2.9.1.2	Change from Baseline in CGM-Derived Hypoglycemia Parameters by Day - Per Protocol Population	14.2.2.9.1.1
14.2.2.9.2.1	Change from Baseline in CGM-Derived Hypoglycemia Parameters by Week - Intent-to-Treat Population	14.2.2.9.1.1
14.2.2.9.2.2	Change from Baseline in CGM-Derived Hypoglycemia Parameters by Week - Per Protocol Population	14.2.2.9.1.1
14.2.2.10.1*	Change from Induction 1 (Baseline visit) in Gold Scale Assessment of Hypoglycemia Unawareness - Intent-to-Treat Population	
14.2.2.10.2*	Change from Induction 1 (Baseline visit) in Gold Scale Assessment of Hypoglycemia Unawareness - Per Protocol Population	14.2.2.10.1
14.3.1.1*	Overview of Adverse Events - Safety Population	
14.3.1.2*	Summary of Treatment-Emergent Adverse Events by System Organ Class, Preferred Term - Safety Population	
14.3.1.3	Summary of Treatment-related Treatment-Emergent Adverse Events by System Organ Class, Preferred Term - Safety Population	14.3.1.2
14.3.1.4*	Summary of Serious Treatment-Emergent Adverse Events by System Organ Class, Preferred Term - Safety Population	14.3.1.2
14.3.1.5	Summary of Treatment-Emergent Adverse Events Leading to Study Discontinuation by System Organ Class, Preferred Term - Safety Population	14.3.1.2

Table Number	Table Title	Shell Number (if repeat)
14.3.1.6	Summary of Serious Adverse Events Leading to Death by System Organ Class, Preferred Term - Safety Population	14.3.1.2

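### Per-day CGM changes are measured against a single pre-dose day although a week of run-in data exists, and the Week 4 CGM endpoint is not tied in words to the weekly derivation

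*SAP*

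**What the plan says.** SAP 4.2.1 words the hypoglycemia endpoints as "Change from baseline to Week 4 in CGM-derived hypoglycemia parameters of" time below, and episode rates at, 70, 60 and 50 mg/dL, plus an area-over-the-curve (AOC) measure. A parallel item covers mean glucose, its standard deviation and time in and above range. SAP 7.10.4 repeats this list.

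SAP 7.2.10 derives these quantities per 24-hour day, counted from the injection. For them, "baseline will be based on the CGM data collected on the latest day prior to the date/time of the first CSGI injection".

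SAP 7.2.10.1 then says: "Additionally, all derived CGM endpoints will be derived on a weekly basis". Its window table defines Week 4 as Days 22 to 28 and the baseline as the 7 days before Day 1. The AOC is an exception: its baseline is one pre-dose reading in both derivations.

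SAP 7.10.4 assigns CGM parameters to a one-factor ANOVA without saying whether the unit is a day or a week. SAP 12 lists by-day and by-week tables, each for ITT and PP; the first is titled "Change from Baseline in CGM-Derived Hypoglycemia Parameters by Day - Intent-to-Treat Population". SAP 7.10.5 treats all secondary endpoints as descriptive, without adjustment for multiple comparisons.

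Protocol 7.1 and 9.5.3 require at least 6 days of recorded CGM data before the baseline induction. Protocol 9.5.3 places a new sensor before the Day 1 clamp and has the first OmniPod deployed during recovery from it.

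**The concern.** A daily change is a difference of two single days, and time below 70, 60 or 50 mg/dL can vary a good deal from one day to the next. Using one baseline day leaves unused, in the daily version, a run-in that subjects were required to record. Because the same day is subtracted from all 28 treatment days, a chance difference between arms on that day reappears on every one of them and can look like a sustained effect.

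The chosen day may also be unrepresentative. First dosing follows the Day 1 clamp, and the SAP does not say whether the latest day is a calendar day or the preceding 24 hours. Because the daily periods run from the injection, the 24-hour reading is plausible, and it would place deliberately induced hypoglycemia in the baseline of a hypoglycemia endpoint.

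Finally, without a sentence naming the tested version, a later reader cannot confirm that the reported Week 4 result was the one planned.

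**Working it through.** **The plan's own figures.** SAP 5 sizes the trial on epinephrine only: "a plasma epinephrine increase compared to placebo of 1.5 nmol/l" with "SD of 1.34 nmol/l at an induced PG of 50 mg/dl". A two-sided 5% t-test gives 78.2% power at 13 per group and 81.3% at 14. So 14 × 3 = 42, which matches the minimum N in the protocol synopsis; 48 are randomized. No SD or effect is given for any CGM endpoint, so the size of this point rests on assumptions.

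**Inputs.** Allocation: "The randomization scheme is 1:1:1 for high dose, low dose and placebo", 16 per group, so the combined comparison is 32 vs 16. Test: two-sided 5%. Assumption: r, the within-subject day-to-day variance s² divided by the between-subject variance t² of true change, is 0.5 to 8, with days independent within a subject.

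**Formulas, in units of t².**
- Day minus one-day baseline: 1 + 2r
- Week minus 7-day baseline: 1 + 2r/7
- Day minus 7-day baseline: 1 + r + r/7
- Correlation of two daily changes sharing one baseline day: (1 + r)/(1 + 2r)

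Power is from the noncentral t at the difference that has 80% power on the weekly version (0.876 of the weekly SD).

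| r | Day-day variance | Week-week variance | Ratio | Power on one day | Day-day ÷ day vs 7-day baseline | Correlation |
|---|---|---|---|---|---|---|
| 0.5 | 2 | 1.143 | 1.75 | 56% | 1.27 | 0.75 |
| 1 | 3 | 1.286 | 2.33 | 45% | 1.40 | 0.67 |
| 2 | 5 | 1.571 | 3.18 | 35% | 1.52 | 0.60 |
| 4 | 9 | 2.143 | 4.20 | 28% | 1.62 | 0.56 |
| 8 | 17 | 3.286 | 5.17 | 23% | 1.68 | 0.53 |

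Changing only the baseline of the daily values thus cuts their variance by a factor of about 1.3 to 1.7.

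**If every day were tested at 5%.** With equicorrelated tests at the correlations above, the chance of at least one false-positive day under no effect, per parameter and comparison, is 29%, 36%, 41%, 45% and 47% over 28 days (r = 0.5 to 8). Over Days 22-28 alone it is 16% to 22%. Independent tests would give 1 − 0.95^28 = 76%, but days that share a baseline are not independent.

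**Sensitivity.** Day-to-day autocorrelation of 0 to 0.6, and between-subject variance of 0 to 2 times the day variance (16 vs 16), give an SD ratio of 1.19 to 2.65 and single-day power of 66% to 19%. The simulated 28-day rate is 27% to 51%.

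**Clamp in the baseline day.** Protocol 9.4 lowers glucose from 70 to 50 mg/dL at about 1 mg/dL per minute (20 minutes). It then holds it for 30 minutes, with a second sample set 10 minutes later (40 minutes). That is about 60 minutes below 70 mg/dL before recovery: 60/1,440 = 4.2% of one day, against 60/10,080 = 0.6% of a week.

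**The case against.** The strongest reply is that the two derivations are not equal candidates. For CGM, Week 4 exists only in the weekly window table. The daily derivation gives 28 day values and nothing called Week 4, so it cannot by itself yield the named endpoint. That stands: what is missing is an explicit link. A reader might infer that the plan leaves two rival Week 4 endpoints open; the window table does not support that.

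A reader might also infer that 28 daily significance tests are planned. The SAP nowhere says that the ANOVA is run by day. In SAP 12 the hormone results have separate tables with ANOVA in the title; the CGM tables do not. The SAP does not exclude daily testing either, so 28 is an upper limit on the count, and only 7 of those days fall in Week 4.

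Nor can the daily version be called far noisier as a fact. The excess depends on an assumed variance ratio, and the SD ratio is as low as 1.19 at one end of the range.

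The consequence is also limited. The endpoints are secondary and declared descriptive, they lie outside the testing hierarchy, and the CGM tables are not marked for the early primary-endpoint output. The weekly version does use the whole run-in.

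What remains is the stated single-day baseline rule, which has no evident advantage over a 7-day baseline that is already being derived, and the possible inclusion of the clamp.

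**Conclusion.** The point holds and is minor. SAP 7.2.10 sets a one-day baseline for the daily CGM changes (AOC aside) when at least 6 recorded days are required. Under the assumed r of 0.5 to 8, a daily change has 1.75 to 5.2 times the variance of the weekly change, and single-day power is 56% to 23% where the weekly version has 80%. About 1.3- to 1.7-fold of the excess variance is removed by changing the daily baseline alone.

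The clamp problem depends on reading the latest day as the 24 hours before first dosing, which the SAP leaves undefined. The clamp precedes treatment in all arms, so it would mainly distort the size of each arm's change and not systematically favor one arm.

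The missing link between the Week 4 endpoint and the weekly derivation is a gap in wording. Confirmatory alpha is unaffected. The practical risks are imprecise daily changes and selective reporting of favorable days, with a false-positive chance of 29% to 47% over 28 days only if every day were tested.

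**What to change.** - SAP 7.2.10: replace the single-day baseline for the daily values with the average over the run-in, that is, the 7 days before Day 1, and state that Day 1 clamp data are excluded. Use the same definition in 7.2.10.1, where the window table counts back from Day 1 but the text counts back from the time of the first injection. The AOC baseline can stay as it is.
- SAP 4.2.1 and 7.10.4: state that the tested Week 4 CGM endpoint is the weekly value for Days 22-28 against that 7-day baseline.
- SAP 12: present the by-day tables and figures as descriptive, without p-values.

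This takes SAP and table-shell wording and a small programming change, with no new data. The cost is the loss of formal day-level tests, which matters little for endpoints already declared descriptive.
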